### **Analytic procedures for cluster matching prior to randomization:**

Using rules designed to prevent spillover/diffusion to villages outside of a cluster, two types of clusters were defined either standalone large towns, which could not be matched with comparable smaller villages, or, more commonly, groups of neighboring villages. Because the total number of clusters available for randomization was too small to assume comparability on covariates/confounders measured or unmeasured, we matched triads of "similar" clusters that could be randomized into ENTR, YRI+ENTR arms and a control arm. Data were available from participant applications to participate in the training opportunities and in the eligibility screening surveys, as well as known data about the municipalities (see list below).

To accommodate the requirements of the study we used a "threshold blocking" (Higgins, Sävje, & Sekhon, 2016), allowing the creation of groups of at least or exactly  $n$  matched items based on a distance measure. Following common practice, we define "similarity" on the basis of distance in a multidimensional space. In this study we used Euclidean distance as a measure of similarity, and we computed it using standardized variables to protect against scale effects.

Procedurally, we implemented the matching by first aggregating the individual-level data up to the cluster level. We produced proportions from binary variables as well as categorical variables with more than two levels (which we split into binary variables). We computed the means of continuous variables and kept indicator variables unchanged. We then used the following variables: age, sex, marital status, number of dependents, education, previous skill training, income generating activities, days and hours worked in the past month, WHO Disability Assessment Schedule (WHODAS) score, Difficulties in Emotion Regulation Scale (DERS) score, locality has access to highway, locality is a hub village, and locality population.

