The goal of this analysis is to determine if there are differences among the three groups assigned at randomization (Control, ENTR, and ENTR+YRI). As described above, all analyses will include the aggregated baseline value of the outcome as a control at the cluster level, and furthermore, of any cluster-level potential treatment confounders shown to be imbalanced across the three groups. In particular we will be looking for group differences in the slopes of the primary outcomes over the lifetime of the study. Fixed effects will be time and group membership and their two-way interaction. Each subject will be measured three times—baseline, post-training, and at 12-month follow up—so we have three repeated measures for each subject, and each set of repeated measures is nested within study cluster. Subject- and cluster-specific slopes and intercepts will be modeled as random effects. We can test for the necessity of the subject and cluster specific slopes through likelihood ratio tests. Evidence of a group differential effects will be if the likelihood ratio test for the time by group interaction is significant at the 0.05 level. For pairwise differences we will examine the regression coefficients and base inference on Wald tests. We will estimate the model with Restricted Maximum Likelihood (REML, also MLR) for testing for random effect parameters and Full Maximum Likelihood (FML or MLF) for fixed effects. We will account for attrition by calculating inverse probability weights and/or multiple imputation. All linear modeling assumptions will be verified, both by

evaluating underlying distributions and model residuals. Approaches to the violation of model assumptions or for non-continuous outcomes include use of response transformations, generalized linear mixed effect models or generalized estimating equations.

We now expand the above model to include possible effect modifiers gender, mental health status at baseline. To the model above we will include a three-way interaction between time, gender, and treatment group. Evidence of a moderating effect will be if likelihood ratio test for the three-way interaction term is significant at the 0.05 level.

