As above, we will use cluster-level controls for aggregated levels of the outcome variable in all analyses, because even including the matching techniques employed, the total number of clusters is too small to assume that randomization will achieve balance on all variables. Furthermore, having tested for cluster-level imbalances in all cluster-level variables assessed at baseline, we will adjust models for any cluster-level confounders judged to have likely influence on the outcomes, for example, economic conditions, where significant imbalance was found. Similarly, individual-level confounders will be assessed in models and can be tested for their influence using multivariate generalized linear hypothesis testing to assess the influence of a group of variables or by means of log-likelihood test comparing nested models as described above.

We can use restricted fence methods as an example of variable selections.

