## **Part II Emotion Regulation as the Mechanism Through which the YRI improvements operate**

**Primary Outcomes:** OMPA internalizing, OMPA externalizing

**Primary Predictor:** Group Membership (Control, ENTR-only, YRI+ENTR)

**Hypothesized Mediator:** Emotion Regulation (assessed by DERS)

**Possible Moderators:** Subject gender, age, education level/literacy, session attendance

We hypothesize that the YRI improvements may operate through changes in emotion regulation. This is a proposed mediation model where the primary predictor is group membership, the primary outcome is mental health at 12 months, and the mediator is emotion regulation as measured by the Difficulties in Emotion Regulation (DERS) at six weeks. We will test for the indirect effect of group membership on Mental Health Status using conditional process analysis (Hayes, 2013). The conditional process equations are (if gender modifies the indirect effect for example):

$$DERS(6\ weeks) = B_0 + a * X$$

$$MH(12\ months) = B_0 + cX + b_1 * DERS(6\ weeks) + b_2 * G + b_3 * G * DERS.$$

Where  $X$  is group membership and  $G$  is gender. The coefficient  $a$  quantifies the effect of group membership on emotion regulation and  $b$  quantifies the effect emotion regulation on mental health independent of group membership. The product  $p = a(b_1 + b_3 * G)$  is the *indirect effect* of group membership on Mental Health. We can test for the significance (null hypothesis  $p = 0$ ) via

bootstrapping. A significant (at 0.05) is indication that emotion regulation mediates the relationship between the YRI effects and mental health. For outcomes that are binary we will need to use the KHB method (Breen, Karlson, & Holm, 2013) to rescale the regression coefficients correctly. A strength of this analysis is that group membership, emotion dysregulation and Mental Health are measured at three different time points which is necessary for causal mediation (though not sufficient).

As an alternative we can test for mediation using Structural Equation Modeling (SEM). This approach is more flexible than conditional process analysis and may allow us to use full-information maximum likelihood (FIML) as opposed to multiple imputation. All causal models will be evaluated for the possible effects of unmeasured confounders (VanderWeele & Ding, 2017).

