### **Data Analysis Plan for Hypothesis 3b:**

*Hypothesis 3(b): Improvements in mental health and functioning due to YRI will lead to (mediate) greater employment outcomes and superior economic self-sufficiency over time.*

**Primary Outcome:** Measures of employment and superior economic sufficiency.

**Primary Predictor:** Group membership.

**Mediator:** Mental Health as measured by the HSCL, OMPA; functioning as measured by WHODAS

**Possible Moderators:** Subject gender, age, education level/literacy, session attendance

Similar to Aim 3(a) we will test for mediation using condition process analysis the process equations are similar:

$$MH(12\ months) = B_0 + a * X$$

$$Employment = B_0 + B_0 + cX + b_1 * MH + b_2 * G + b_3 * G * MH$$

The indirect effect of mental health on employment and economic self-sufficiency is quantified by the product  $p = a(b_1 + b_3 * G)$ . We will use a bootstrap test to access significance. Binary outcomes will need to be adjusted using KMB method. The size and direction of effects will be determined by the estimates of the regression coefficients.

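### The mediation equations do not require adjustment for measured individual baseline common causes, so mediation can be declared too often when the mediator has no effect on the outcome

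*Combined protocol and SAP*

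**What the plan says.** **Mediation equations.** Under Data Analysis Plan for Hypothesis 3b, the mediator model is "MH(12\ months) = B_0 + a * X" and the outcome model is "Employment = B_0 + B_0 + cX + b_1 * MH + b_2 * G + b_3 * G * MH", where G is gender. On testing, the plan says: "We will use a bootstrap test to access significance". Part II of the Hypothesis 3a plan has the same structure with DERS as mediator, and sets the criterion: "A significant (at 0.05) is indication that emotion regulation mediates the relationship between the YRI effects and mental health". The Hypothesis 3c plan prints the 3b equations again.

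**Cluster-level covariates.** The cluster-matching section and the Hypothesis 3a plan require the cluster mean of the baseline outcome in every analysis. Other cluster-level confounders depend on imbalance. The 3a plan adds control "of any cluster-level potential treatment confounders shown to be imbalanced across the three groups", and later adjusts for influential cluster-level confounders, "for example, economic conditions, where significant imbalance was found".

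**Individual-level covariates.** The 3a plan also says that individual confounders will be assessed and may be tested for influence, with no balance condition. It lists no variables, and the sections on mediation do not refer back to it.

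**What was measured.** The matching variables include "age, sex, marital status, number of dependents, education, previous skill training, income generating activities, days and hours worked in the past month", as well as WHODAS and DERS scores.

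**Sensitivity analysis.** Part II states: "All causal models will be evaluated for the possible effects of unmeasured confounders".

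**The concern.** The indirect effect is the product of a (group to mediator) and b (mediator to outcome). Randomising clusters protects a. It does not protect b, because two youths in the same arm differ in mental health for reasons such as schooling, dependents or work history, and these can also affect employment. A variable can be perfectly balanced across arms and still bias b, so an imbalance trigger asks the wrong question for this path. Cluster aggregates cannot help with differences between youths in the same cluster.

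The emotion-regulation mechanism, Hypothesis 3b and Hypothesis 3c all rest on this product. If YRI does improve mental health, a confounded b can be reported as YRI acting on employment through mental health when no such path exists. Confounding of opposite sign could instead hide a real path.

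**Working it through.** The plan states no sample size, ICC, effect size or error rate, so there is no figure of its own to reproduce. All numerical inputs below are assumptions.

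**1. Bias formula.** Let mental health and employment have unit SD within arm, let true b = 0, and let a baseline covariate C have standardised effects r on mental health and s on employment. Then

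- fitted b → r × s
- false indirect effect → a × r × s

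For r = s = 0.3 and a = 0.4: b → 0.3 × 0.3 = 0.09, and the indirect effect → 0.4 × 0.09 = 0.036. Simulation gave 0.089 and 0.036. The bias does not shrink with sample size, so a larger trial detects the false effect more reliably.

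**2. Simulation under the 3b equations.** Three arms, cluster randomisation, ICC 0.05, continuous outcome, cluster-robust standard errors, Monte Carlo interval for the product, 400 runs per cell, true b = 0. The table gives the rate of declaring mediation with the equations as printed.

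| N (clusters) | a | r, s = 0.2, 0.2 | 0.3, 0.3 | 0.5, 0.3 |
|---|---|---|---|---|
| 300 (30) | 0.2 | 2% | 8% | 14% |
| 300 (30) | 0.4 | 6% | 21% | 46% |
| 585 (45) | 0.2 | 4% | 15% | 28% |
| 585 (45) | 0.4 | 13% | 45% | 82% |
| 1215 (45) | 0.2 | 12% | 37% | 50% |
| 1215 (45) | 0.4 | 25% | 78% | 96% |

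- No confounder (r = s = 0): 0–5%, so the test itself is sound.
- a = 0: at most about 5% as printed.

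**3. Do the plan's rules help?** At N = 1215, a = 0.4:

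- Adding the mandatory cluster mean of the baseline outcome: 26% / 78% / 97%.
- Adding the imbalance rule: 25% / 78% / 97%. It selected C in only 3–7% of trials.
- Keeping C when an individual-level influence test is significant: 0–5% in every cell.
- Entering C in both equations regardless: 0–5% in every cell.

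A percentile cluster bootstrap, closer to the planned test (200 runs, N = 1215, a = 0.4, cluster mean included), gave 5% with no confounder, 86.5% at (0.3, 0.3) and 95% at (0.5, 0.3). With C entered, the last two fell to 7.5% and 7.0%.

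**4. Are a youth's own baseline mediator and outcome enough?** A separate simulation used two arms, 10 clusters of 40 per arm, ICC 0.03, a = 0.3, r = s = k, and joint significance of a and b on 18 df.

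| k | As printed | Plus own baselines | Plus own baselines and C |
|---|---|---|---|
| 0.2 | 14–17% | 5–6% | 3–5% |
| 0.3 | 53% | 10–24% | 3–5% |
| 0.4 | 77–78% | 23–55% | 3–5% |

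The higher values in the middle column apply when baseline employment says little about C. With binary employment at k = 0.3 the three figures were 38%, 14% and 4%. Own baselines therefore help but do not replace the covariates.

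**5. Hand check of the 53%.** N = 2 × 10 × 40 = 800.

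- b: SE ≈ 1/√800 = 0.035; 0.09/0.0354 = 2.55. Against a critical value of 2.10, the chance of significance is Φ(0.45) ≈ 0.67.
- a: design effect 1 + 39 × 0.03 = 2.17; SE ≈ √(4 × 2.17/800) = 0.104; 0.3/0.104 = 2.88. The chance is Φ(0.78) ≈ 0.78.
- Both: 0.67 × 0.78 ≈ 0.52, in line with the simulation.

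**The case against.** The strongest reply is that the plan already has the right tool. Its individual-level rule turns on influence, not balance, and in simulation it worked as well as forcing the covariate in. It sits in the Hypothesis 3a plan, of which the emotion-regulation analysis is Part II, and the 3b plan says it proceeds as 3a does. So a reader might infer that the plan's whole covariate policy depends on imbalance, but the documents do not support that: only the cluster-level rule does. What remains is that the individual rule is permissive, names no variables and is not restated for any mediation model. An analyst could follow the plan in full and fit the printed equations.

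The equations are also schematic. Gender is an example, and the mandatory cluster mean is printed in none of them. This stands, but adding that mean changes little.

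A reader might infer that education is shut out of the employment equation. The documents do not show that. Education/literacy is a listed moderator, the printed outcome equation gives the moderator a main effect, and the 3c plan allows all moderators together. The 3c text, however, describes moderation of the group-to-mediator path, so its text and its equation differ. Prior work, training, dependents and marital status are on no mediation moderator list.

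Nor does every confounded b yield a significant product: with weak paths and small N the rate stays below 5%. The simulations do not model the planned false discovery rate adjustment, which addresses multiplicity and does not remove bias. Part II also concedes that time ordering alone does not establish causal mediation, but it adds no covariate set. The planned sensitivity analysis concerns unmeasured confounders and is no substitute for adjusting for measured ones.

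**Conclusion.** The concern holds in this form: the mediation models do not require adjustment for measured individual-level baseline common causes of mediator and outcome, and the covariates that are mandatory do not do that job. Mediation can then be declared too often when the mediator does nothing, provided YRI moves the mediator.

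The 2–96% range as printed, and the 0–7% after adjustment (7.5% at most, in a 200-run check), depend on assumed N, cluster numbers, ICC, a and confounder strength. They show direction and range and are not this trial's error rate. The sign and strength of confounding by education or work history are likewise assumed. The structural conclusion needs only that some measured baseline variable affects both mediator and outcome. The plan should be changed, because the remedy is nearly free and removes a bias that the printed models carry.

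**What to change.** In Part II of the Hypothesis 3a plan and in the 3b and 3c plans, state that:

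- Both the mediator and the outcome equation will include, whatever the balance across arms, a fixed set of individual baseline covariates: sex, age, marital status, dependents, education/literacy, earlier skills training, income-generating work, and days and hours worked.
- Both will also include each youth's own baseline mediator and outcome where measured (including DERS and WHODAS), plus district and locality type.
- Any baseline variable used as a moderator W also enters the outcome equation as a main effect. Session attendance arises after randomisation and is excluded from this rule.

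Limit the imbalance trigger in the cluster-matching section and the 3a plan to the comparisons between arms.

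The cost is SAP wording. Apart from literacy, which is listed only as a moderator, the named individual covariates were available from applications or screening and were used for matching. The price is around ten extra individual-level parameters per equation, more where a variable has several categories, and indirect effects may come out smaller.

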### **Data Analysis Plan for Hypothesis 3c:**

*Hypothesis 3(c): Homelessness, orphanhood, young parenthood, and high problems in emotion regulation comorbid with other mental health conditions will be moderators lessening the effectiveness of YRI.*

**Primary Outcome:** Measures of employment and superior economic sufficiency

**Primary Predictor:** Group Membership

**Mediator:** Mental Health

**Possible Moderators:** Subject gender, age, education level/literacy, session attendance, emotion regulation.

To the mediation model described in hypothesis 3b we will add terms to account for the moderating influences of gender, age, education level/literacy, session attendance, and emotion regulation. For purposes of exposition we will generically label the moderator as  $W$ . Our hypothesis is that moderators act on the influence of group membership and mental health. The conditional process equations in this case are (only one moderator was included for brevity):

$$MH(12\ months) = B_0 + a * X$$

$$Employment = B_0 + B_0 + cX + b_1 * MH + b_2 * G + b_3 * G * MH$$

In these equations the indirect effect of group membership on employment and economic self-sufficiency is  $(a_1 + a_3 * W) * b$ . The value  $a_3 * W * b$  is sometimes called the index of moderated mediation. In the case of dichotomous  $W$  (gender, homelessness, young parenthood) this value reduces to  $a_3 * b$  and is interpreted as the difference of the indirect effect of group membership on employment and economic self-sufficiency of the two  $W$  groups. Test for moderation can be directly from the coefficient  $a_3$ . Alternative tactics include SEM as opposed to conditional process equations. KHB rescaling will be needed since moderators, mediators, and outcomes represent different variable types (binary, continuous etc.). In practice we can include all moderators in the model simultaneously.

We can also verify which path the candidate variables modify (we assumed the path from primary predictor to mediator). This can be done in the context of SEM models. We can fit models where the moderators act on the paths from mediator to outcome or both. Using fit indices such RMSEA we can compare model fits to determine which model best matches the data.

**Missing Data:** Using ITT principle we will obtain estimates of missing values of all study participants and at all time points. We will primarily use multiple imputations through chained equations. Missing data may exist at items within scales and we will use the Plumptre method (ref needed). Furthermore, where supported by our software, we can combine the use of imputations with attrition weighting. We will report both percentage of missing data and percentage of complete cases. For SEM models we can employ FIML to address missingness .

**Multiple Comparisons:** We will use False Discovery Rate (FDR) (ref needed) to adjust for multiple comparisons within hypothesis. This is necessary since we will be comparing multiple models.

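### Hypothesis 3c is printed with the Hypothesis 3b equations, so its named test (`a_3`) has no parameter; three of its four moderators are not among the terms to be added, and session attendance is

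*Combined protocol and SAP*

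**What the plan says.** All references are to the combined protocol and SAP.

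**Equations.** The Hypothesis 3b plan models mental health at 12 months as `B_0 + a*X` and employment as "Employment = B_0 + B_0 + cX + b_1 * MH + b_2 * G + b_3 * G * MH". It gives the indirect effect as `a(b_1 + b_3*G)`. The Hypothesis 3c plan prints the same pair, including the doubled intercept. It then says "In these equations the indirect effect of group membership on employment and economic self-sufficiency is" `(a_1 + a_3*W)*b`, and "Test for moderation can be directly from the coefficient" `a_3`. On which path is moderated, it says "we assumed the path from primary predictor to mediator". Models with moderators on other paths may also be fitted in SEM: "Using fit indices such RMSEA we can compare model fits to determine which model best matches the data".

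**Moderators.** Hypothesis 3c names four: young parenthood, homelessness, orphanhood, and severe emotion-regulation problems that occur together with other mental health conditions. The analysis text says "we will add terms to account for the moderating influences of gender, age, education level/literacy, session attendance, and emotion regulation", and the Possible Moderators line gives the same five. Two of the hypothesised four return only as examples of a dichotomous W: "gender, homelessness, young parenthood) this value reduces to" `a_3*b`.

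**Session attendance.** It is a possible moderator in the Aim 3 table and in the plans for Hypotheses 3a (including Part II), 3b and 3c. The section on cluster matching describes the control arm as untreated.

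**The concern.** One pair of equations cannot have two different indirect effects. Hypothesis 3b reads the pair as moderation of the effect of mental health on employment. Hypothesis 3c reads it as moderation of the effect of group on mental health. The coefficient that carries the Hypothesis 3c test is in neither equation.

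The moderator list has a similar gap. An analyst who works from the committed terms would test gender, age and education, which Hypothesis 3c does not mention, and would leave out most of what it does mention. Attendance is a different kind of variable from the rest: it is observed after allocation, and one arm has no sessions to attend.

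At stake is whether Hypothesis 3c can be tested as stated, with a moderated path and a moderator set fixed before the data are seen.

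**Working it through.** The plan gives no figure for this point, so the check is structural. Any coefficient values below are assumed for illustration.

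**1. The two plans side by side**

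| | Hypothesis 3b | Hypothesis 3c |
|---|---|---|
| Mediator equation | `B_0 + a*X` | the same |
| Interaction in the outcome equation | `b_3*G*MH` | the same |
| Stated indirect effect | `a(b_1 + b_3*G)` | `(a_1 + a_3*W)*b` |
| Path moderated | mediator to outcome | group to mediator |
| Named test | bootstrap of the product | `a_3` |

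Writing `a` for `a_1` and `b_1` for `b` is only notation. The missing `W` and `X*W` terms in the mediator equation are not. In Part II of the Hypothesis 3a plan, G is gender; on that reading no Hypothesis 3c moderator is in the printed equations at all.

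**2. What the printed equations return if G is read as W**

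Suppose `MH = B0 + a1*X + a2*W + a3*X*W + error` and `Employment = B0 + c*X + b*MH + b2*W + error`. Assume a binary W independent of arm, independent errors, and no moderation of the direct effect or of the mediator-to-outcome path.

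- Regressing MH on X alone gives `a = a1 + a3*P(W)`.
- The true outcome model has no `W*MH` term, so `b_3 = 0`.
- The printed difference in indirect effect is therefore `a*b_3 = 0` for every value of `a3`. The true difference is `a3*b`.

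Illustration with a1 = -0.5, a3 = 0.3, b = -0.4 and P(W) = 0.5:

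- True indirect effects: (-0.5)(-0.4) = 0.20 at W = 0, and (-0.5 + 0.3)(-0.4) = 0.08 at W = 1. The difference is -0.12.
- Printed: a = -0.5 + 0.3 × 0.5 = -0.35, so the indirect effect is (-0.35)(-0.4) = 0.14 in both groups. The difference is 0.

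A least-squares fit to 2,000,000 simulated records agreed. The printed equations gave 0.141 and 0.141; the model with `X*W` gave 0.201 and 0.081, a difference of -0.120.

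**3. Moderators hypothesised against moderators analysed**

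| Hypothesis 3c moderator | Among the five terms to be added? | Elsewhere in the Hypothesis 3c analysis text? |
|---|---|---|
| Homelessness | No | Example of a dichotomous W |
| Young parenthood | No | Example of a dichotomous W |
| Orphanhood | No | No |
| Severe emotion-regulation problems with comorbidity | Emotion regulation only | No comorbidity condition, no time point |

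The time point matters because DERS at six weeks is the mediator in Part II.

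**4. Arm-by-attendance design**

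The six columns are the intercept, E (ENTR-only), Y (YRI+ENTR), A (attendance), `E*A` and `Y*A`.

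- *Total attendance, A = 0 in control.* Then `E*A + Y*A = A`, one dependency, and the rank is 5. The attendance slope in control is undefined, so neither contrast with control is estimable. The slope difference between YRI+ENTR and ENTR-only is.
- *YRI sessions only.* Then `E*A = 0` and `Y*A = A`, and the rank is 4. None of the three contrasts is estimable.

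The plan does not say which sessions are counted.

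**The case against.** **The intended model is already in the prose.** The text adds terms to the Hypothesis 3b model, labels the moderator W, gives a formula that fits only one path, and names that path. The doubled intercept was copied too. This stands, and it makes the equation fault a correctable slip. It does not settle the moderator set or attendance.

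**A reader might infer that the sponsor will test Hypothesis 3c with `a*b_3` and so miss the moderation.** The documents do not support that: `a*b_3` is never named as the Hypothesis 3c test, and an analyst told to test `a_3` would probably notice that the term is absent. The zero in the working shows that the printed model is the wrong one. It does not predict what will be done. It also rests on linear models, whereas the plan expects some binary outcomes with KHB rescaling. A loss of power cannot be stated, because the documents give no sample size, cluster count or effect size.

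**A reader might infer that three moderators were abandoned.** That is also too strong. The section opens by restating all four, two are named as examples of W, and the text allows all moderators to be entered together. The Hypothesis 3a material names baseline mental health status and high comorbidity as modifiers. These narrow the gap but do not define the Hypothesis 3c terms, and orphanhood still has no analysis text.

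**Attendance is mostly listed only as a possible moderator, and can be analysed within the active arms.** True for total attendance, so it would be wrong to call the interaction unidentified altogether. But the Hypothesis 3c text commits to adding the term, and even the estimable contrast mixes effect modification with who chooses to attend.

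**Choice of path is optional, and the false discovery rate is controlled within hypothesis.** That control needs a defined set of tests. Here neither the moderators nor the path is fixed.

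**Conclusion.** The Hypothesis 3c analysis is wrong as written and should be corrected. The named test has no parameter in the printed equations. Three of four hypothesised moderators are outside the five committed terms: two survive as examples and one only in the hypothesis statement. The fourth is listed without its comorbidity condition or a baseline time point. An arm-by-attendance term is not identified against control under either definition of attendance, and between the active arms it is estimable only for total attendance and open to self-selection.

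The statements about equations and lists rest on the text alone. The result `b_3 = 0` rests on the assumptions given in step 2 of the working. The rank results need only that control youth have no sessions.

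A reader might extend this to the trial's main effectiveness analysis. The documents give no ground for that: the group-by-time tests under Hypothesis 3a use none of these equations. The damage is confined to Hypothesis 3c and the attendance entries.

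**What to change.** 1. Print `MH = B0 + a1*X + a2*W + a3*X*W` and `Employment = B0 + c*X + b*MH + b2*W`. Enter X as two arm indicators, and carry over the plan's clustering and cluster-level baseline control. Keep `a3` as the test. Report it for YRI+ENTR versus ENTR-only, which isolates YRI, and for YRI+ENTR versus control. Keep KHB for binary outcomes.
2. Make the Hypothesis 3c moderators homelessness, orphanhood, young parenthood, and high baseline DERS with comorbidity, all measured at baseline. Define the DERS cut-off and the qualifying conditions. Keep gender, age and education/literacy as secondary moderators.
3. Take session attendance out of the moderator lists in the Aim 3 table and in the plans for Hypotheses 3a (including Part II), 3b and 3c. Report it only as an exploratory adherence analysis within the active arms, stating which sessions are counted.
4. Label the SEM fits on other paths and their RMSEA comparisons exploratory.

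An `X*W` term in the outcome equation and a bootstrap interval for `a3*b` are optional.

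The cost is SAP wording and analysis code, provided that the four moderators were recorded at baseline.

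### Hypothesis 3c: the index of moderated mediation is written as a_3*W*b, which is not a single number unless W is coded 0/1; the index should be the slope a_3*b

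*Combined protocol and SAP*

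**What the plan says.** The point concerns the combined protocol and SAP, section on the data analysis plan for Hypothesis 3c.

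- The hypothesis reads: "Homelessness, orphanhood, young parenthood, and high problems in emotion regulation comorbid with other mental health conditions will be moderators" that lessen the effectiveness of the intervention.
- The analysis adds "the moderating influences of gender, age, education level/literacy, session attendance, and emotion regulation" to the Hypothesis 3b mediation model. The section's list of possible moderators matches: "Subject gender, age, education level/literacy, session attendance, emotion regulation".
- The indirect effect is given as `(a_1 + a_3*W)*b`, and `a_3*W*b` is "sometimes called the index of moderated mediation".
- For a dichotomous W the section says this becomes `a_3*b`, which "is interpreted as the difference of the indirect effect of group membership on employment and economic self-sufficiency of the two" W groups.
- On testing: "Test for moderation can be directly from the coefficient" `a_3`.
- The moderated path is the first stage: "we assumed the path from primary predictor to mediator".
- The printed mediator equation is "MH(12\ months) = B_0 + a * X". It has no W and no X*W term. The only interaction printed is G*MH, in the employment equation.

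The section does not give the coding, centring or unit of any W, or a value of W at which `a_3*W*b` would be evaluated.

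**The concern.** An index of moderated mediation should be one number that says how much the indirect effect changes with the moderator. The expression given contains W itself, so for any moderator with more than two values it is a function, not an index. Treating `a_3*b` as a special case for dichotomous W suggests that continuous moderators need something different, and they do not.

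This affects the estimate of how far the indirect effect on employment and economic self-sufficiency, both listed as primary outcomes under Aim 3, differs across youth. `a_3*W*b` is the only size-of-moderation quantity the section offers. Read literally, it gives a non-binary moderator no single value, and its sign can depend on where W is centred although the hypothesis is directional. It also cannot be set beside `a_3*b` for homelessness, orphanhood or young parenthood.

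**Working it through.** The plan states no figure here, so there is none to reproduce. The check is algebra on the plan's own formula, followed by an illustration.

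**Slope.** Write IE(W) = (a_1 + a_3\*W)\*b. Then dIE/dW = a_3\*b, the same at every W and for every type of W. Also IE(W) - IE(0) = a_3\*W\*b. The plan's expression is therefore the contrast with W = 0.

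**Change of origin.** Let W' = W - c. Then a_3' = a_3 and a_1' = a_1 + a_3\*c.
- a_3'\*b = a_3\*b: unchanged.
- a_3'\*W'\*b = a_3\*W\*b - a_3\*c\*b: shifted.
- (a_1' + a_3'\*W')\*b = (a_1 + a_3\*W)\*b: unchanged.

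**Change of unit.** Let W' = k\*W. Then a_3' = a_3/k.
- a_3'\*W'\*b = a_3\*W\*b: unchanged.
- a_3'\*b = a_3\*b/k: changed, so the index needs its unit stated.

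**Illustration.** Assumed, not from the documents: a_3 = 0.02 per year of age, b = 0.5, ages 18 to 30.

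| Coding of age | a_3\*b | a_3\*W\*b at 18 | at 24 | at 30 | 30 minus 18 |
|---|---|---|---|---|---|
| Years | 0.02 × 0.5 = 0.01 | 0.18 | 0.24 | 0.30 | 0.12 |
| Months (k = 12) | 0.01/12 = 0.00083 | 0.18 | 0.24 | 0.30 | 0.12 |
| Years, centred at 24 | 0.01 | -0.06 | 0 | 0.06 | 0.12 |

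The conditional indirect effect at age 18 is a_1\*b + 0.18 in years. Centred, a_1' = a_1 + 0.02 × 24 = a_1 + 0.48, so it is (a_1 + 0.48) × 0.5 - 0.06 = a_1\*b + 0.18 again. The contrast between two stated ages, 0.12, is also the same under every coding.

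**Binary W.** With 0/1 coding, IE(1) - IE(0) = a_3\*b, as the plan says. With 1/2 coding the difference is still a_3\*b, but a_3\*W\*b is a_3\*b in one group and 2\*a_3\*b in the other. With -1/+1 coding the difference is 2\*a_3\*b, so a_3\*b is half of it. The plan's statement therefore needs the 0/1 coding made explicit.

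**What the test of a_3 covers.** a_3 describes moderation of the group-to-mediator path. The change in the indirect effect is a_3\*b: with a_3 = 0.02 it is 0.01 per year if b = 0.5 and 0 if b = 0. A test of a_3 alone gives no estimate or interval for that change.

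**Printed equations.** They contain no W, a_1 or a_3. Taken literally, their indirect effect is a\*(b_1 + b_3\*G), the form given for Hypothesis 3b, with moderation on the mediator-to-outcome path. The text assumes the other path. The remark that only one moderator is shown for brevity does not explain this, because the interaction is in the wrong equation for the stated assumption.

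**The case against.** The strongest reply is that this is a slip of labelling with no effect on inference. Moderation is tested on a_3, the conditional indirect effect formula is correct for first-stage moderation, and no p-value or conditional effect changes. The moderators in the hypothesis are largely yes/no: homelessness, orphanhood and young parenthood are, and the emotion regulation item is worded as high problems with comorbidity, which may be a status and not a score. The plan gives `a_3*b` for those. Dummy-coded education also reduces to `a_3*b`. All of that stands, and it limits the point to moderators entered as scores or counts.

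A reader might infer three stronger things that the documents do not support:

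- **That the expression depends on the unit of W.** It does not. A unit change cancels in `a_3*W*b`; only a change of origin moves it. The correct index `a_3*b` is the one that carries a unit.
- **That the reported size of moderation will be wrong.** The section gives the expression a name but does not commit to reporting it. The nearest statement on effect size, under Hypothesis 3b, points to the regression coefficients.
- **That the ratio of `a_3*W*b` to `a_3*b` measures the error.** The two are different quantities, a contrast with zero and a per-unit slope. As the table shows, the contrast between two stated ages comes out the same either way.

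What the reply does not remove is that the test of a_3 leaves b out, and that the only quantity offered for the size of the moderated indirect effect is not a single number for the non-binary moderators the section adds.

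**Conclusion.** The point holds as a misdefinition with a limited consequence. By the plan's own indirect-effect formula the index is `a_3*b` for every moderator. For moderators not coded 0/1, `a_3*W*b` varies with W and with where W is centred. It cannot serve as a single size of moderation or be compared with the values for the binary moderators.

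The consequence is an ambiguous estimate and interval for the moderated indirect effect. It is not a wrong test or a wrong conditional effect. No numerical size can be given from the documents, because they state no coefficients, age range or coding; the figures above are illustrative only. The conclusion assumes first-stage moderation that is linear in W, as the section's text states, and that at least one of age, session attendance, education/literacy or emotion regulation enters as something other than a 0/1 variable. The section does not say how these are coded, although it does say that moderators, mediators and outcomes include continuous as well as binary types.

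**What to change.** In the Hypothesis 3c section:

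1. Write the first-stage equation with the terms the text relies on: MH(12 months) = B_0 + a_1\*X + a_2\*W + a_3\*X\*W. Remove the G\*MH interaction from the employment equation, or present it as the alternative second-stage model that the section already mentions.
2. Define the index as `a_3*b` for every moderator. Because group membership has three levels, give one a_3, and so one index, for each arm contrast.
3. State the coding and unit of each W: 0/1 for binary moderators; per SD or between two stated values for continuous ones; one index per level against a named reference for categories. State any centring.
4. Report each index with a bootstrap interval, alongside the test of a_3.
5. Keep `(a_1 + a_3*W)*b` for conditional indirect effects only, at values of W fixed in advance.

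The cost is SAP wording and a little extra output. No new data are needed. The X\*W term must be in the fitted model, which the text intends but the printed equations omit.
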